### Duration of the Study

The study period for each subject is expected to be 14 months, including up to 28 days for screening prior to the first infusion, 12 months of study infusions, a follow-up visit at the infusion cycle month (21 or 28 days) to collect safety and efficacy data for viral marker tests (see Sections 5.8.7 of Study Protocol for additional details).

### Investigators and Study Centers

---

[REDACTED]

[REDACTED]

[REDACTED]

A sufficient number of study sites to enroll up to 50 subjects to obtain at least 26 adult subjects, at least 8 adolescent subjects and at least 8 child subjects will be recruited. Subjects who withdraw (or are withdrawn) will not be replaced.

Randomization and Stratification

Not applicable.

Blinding

Not applicable.

Treatment Regimens

All subjects will receive intravenous infusions of investigational product at the same dose and interval as used for their previous IGIV maintenance therapy. GC5107 will be administered at a dose of 300 - 900 mg per kg (of body weight) every 21 or 28 days ( $\pm 4$  days) for a period of 12 months.

Visit Schedule

The Table 1 below summarizes the timeline for the study. For detailed visit schedule, please refer to the study protocol for GC5107B\_P3 (Section 5.8).

Table 1: Study Timeline

Procedure 28 day regimen (21 day regimen in parentheses)	Time	
Screening*	Day -28 to Day -1 (Day -21 to Day -1)	Up to 28 days prior to the first infusion
Infusion 1	Week 0, D1 Baseline	12 months of infusions
Infusion 2-4 (Infusion 2-4)	Week 4 – 12 (Week 3-9)	
PK Assessment Infusion 5 (Infusion 5)	Week 16 (Week 12)	
Infusion 6 – 13 (Infusion 6 - 17)	Week 20 – 48 (Week 15- 48)	

Follow-up: 4 weeks after last infusion (3 weeks after last infusion)	Week 52 (Week 51)	3 or 4 weeks after the last investigational product infusion
--	----------------------	--

Note: The screening procedures can occur only after a potential subject has signed the ICF. Results of screening must be obtained before the first study infusion.

## 4 STATISTICAL METHODS

### 4.1 Data Quality Assurance

All tables, figures and data listings to be included in the report will be independently checked for consistency, integrity and in accordance with [REDACTED].

### 4.2 General Presentation Considerations

‘Baseline’ is defined as the last available pre-treatment assessment, unless specified in later section. ‘End of Study’ is defined as the last available post-treatment assessment. ‘Treatment Day’ will be calculated relative to the date of the first infusion of GC5107, i.e. Treatment Day = Assessment Date - First Infusion Date + 1 (if on or after day of first infusion); or Treatment Day = Assessment Date - First Infusion Date (if before day of first infusion).

Continuous data will be summarized in terms of the mean, standard deviation (SD), median, minimum, maximum and number of observations, unless otherwise stated. Continuous data that are expected to be skewed will be presented in terms of the maximum, 75% quantile, median, 25% quantile, minimum and number of observations. The minimum and maximum will be reported to the same number of decimal places as the raw data recorded in the database. The mean, median, lower quartile and upper quartile will be reported to one more decimal place than the raw data recorded in the database. The SD will be reported to two more decimal places than the raw data recorded in the database. In general, the maximum number of decimal places reported shall be four for any summary statistic.

Categorical data will be summarized in terms of the number of subjects providing data at the relevant time point (n), frequency counts and percentages. . Any planned collapsing of categories will be detailed in the SAP text and the data displays.

Percentages will be presented to one decimal place. Percentages will not be presented for zero counts. Percentages will be calculated using N as the denominator unless otherwise indicated. If sample sizes are small, the data displays will show the percentages, but any textual report will describe frequencies only.

Changes from baseline in categorical data will be summarized using shift tables where appropriate. For continuous variables, actual values and changes from baseline will be summarized using descriptive statistics across infusion schedule and overall by visit.

P-values greater than or equal to 0.001, in general, will be presented to three decimal places. P-values less than 0.001 will be presented as “<0.001”.

Confidence intervals will be presented to one more decimal place than the raw data.

All report outputs will be produced using SAS® version 9.3 or a later version in a secure and validated environment.

### 4.3 Study Subjects

#### 4.3.1 Disposition of Subjects

A clear accounting of the disposition of all subjects who enter the study will be provided, from screening to study completion.

The following subject data will be presented by infusion schedule and overall:

- A summary of the number of subjects screened for entry into the study and the number and percentage of subjects excluded prior to the first infusion of GC5107 by major reason and overall (Analysis population: All Subjects)
- A summary of the number of subjects treated (with at least one dose of study medication) per center (Analysis population: All Subjects Enrolled)
- A summary of the number and percentage of subjects treated (with at least one dose of study medication), withdrawing after enrollment but prior to first infusion, withdrawing after first infusion and completing each visit of the study. (Analysis population: All Subjects Enrolled). Withdrawals after enrollment but prior to first infusion and withdrawals after first infusion should also be summarized by major reason.

In addition, by-subject listings of eligibility details, visit dates and withdrawal/study completion details (including reason for discontinuation and duration of treatment prior to discontinuation) will be provided.

#### 4.3.2 Protocol Deviations

Protocol deviations will be identified on an ongoing basis by the clinical study team and assessed as “minor” or “major” in consultation with the Sponsor. Major protocol deviations are defined as those deviations from the study protocol that are likely to have an impact on the subject’s rights, safety, well-being, and/or on the validity of the data for analysis. The impact of major protocol deviations on the efficacy and/or safety results will be investigated by assessing the robustness of the study results and conclusions to the choice of analysis population (see Section 4.4), both including and excluding data potentially affected by major protocol deviations.

Protocol deviations and any action to be taken regarding the exclusion of subjects or affected data from specific analyses are defined in Protocol Deviation Specification (PD Spec).

A summary of the number and percentage of subjects with a major protocol deviation by type of deviation will be given by infusion schedule and overall (Analysis population: All Subjects Enrolled). A by-subject listing of major protocol deviations will also be provided.

#### 4.4 Analysis Populations

The primary safety and efficacy analysis will be based on the intention-to-treat (ITT) population. The ITT population will consist of all subjects who are enrolled into the study and received any amount of investigational product.

The per-protocol (PP) population will also be analyzed for efficacy. The PP population will consist of all subjects in the ITT population who complete the whole 12-month study period and who do not have any major protocol violations, which are likely to have an impact on the validity of the data for analysis.

The intention-to-treat (ITT2) second population will consist of all ITT subjects who are enrolled into study following Protocol Version 2.0 amendment 1 (March 16, 2017) onwards. Subjects who are enrolled into study following Protocol Version 1.0 amendment 3 will be excluded. Protocol Version 2, Amendment 1 REB approval dates of each site is listed in Appendices. This population will be used to perform a sensitivity analysis for the assessment of the primary efficacy and safety endpoint.

All PK analyses will be based on the PK population. The PK population will be defined as a subset of adult and adolescent subjects in the ITT population who participate in the PK study and have at least one PK sample collected. At least 20 adult and adolescent subjects will be in the PK population. Blood samples required for PK analysis will be taken before and after the 5th study infusion for those subjects who consent to the PK portion of the study.

Upon database release, protocol deviation and analysis population outputs will be produced and will be sent to the Sponsor for review. An analysis population classification meeting (data review meeting) will be arranged to discuss the outputs and to decide which subjects and/or subject data will be excluded from certain analyses. Decisions made regarding the exclusion of subjects and/or subject data from analyses will be documented and approved by the Sponsor.

A summary of the number and percentage of subjects completing each visit of the study will be given overall for each analysis population (Analysis population: All Subjects Enrolled).

A by-subject listing of analysis population details will also be provided. This listing will be presented overall and will include: center, subject identifier, inclusion/exclusion flag for each population and reason for exclusion from each population. All subjects enrolled will appear on this listing. If subject data has been partially excluded, visit will also appear on this listing.

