## 3 INVESTIGATIONAL PLAN

This will be a prospective, open-label, single-arm, multicenter, historically controlled, Phase III study measuring the safety, efficacy, PK, and tolerability of GC5107 in subjects with PHID.

- The study design is an open-label, uncontrolled study of at least 26 adult subjects, at least 8 adolescent subjects aged  $\geq 12$  to  $< 17$  years and at least 8 child subjects aged  $\geq 2$  to  $< 12$  years with well-defined PHID.
- To guard against dropout and to assure more than adequate power, up to 50 subjects will be enrolled.
- All subjects will be followed for 12 months during which infusions will be given every 21 or 28 days.
- To demonstrate efficacy, the serious bacterial infection rate will be required to have an upper one-sided 99% confidence limit less than 1.0 per subject per year.
- Pharmacokinetics will be determined after the 5th study infusion.

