## 4.7 Efficacy Evaluation

### 4.7.1 Analysis and Data Conventions

Confidence intervals will be calculated at the two-sided 95% level of confidence except for the primary efficacy and safety endpoints which will be one-sided 99% and 95% respectively.

This study is designed to test for non-inferiority of GC5107 which will be compared with historically-based standards. The null hypothesis is that the incidence of serious acute bacterial infections in subjects treated with GC5107 is greater than or equal to 1.0 per subject per year. The alternative hypothesis is that the incidence of serious acute bacterial infections is less than 1.0 per subject per year. Symbolically, this is expressed as follows:

H0: average incidence of serious acute bacterial infections on GC5107  $\geq$  1.0 per subject per year

H1: average incidence of serious acute bacterial infections on GC5107  $<$  1.0 per subject per year

A one-sided test based on a generalized linear models procedure for Poisson regression with  $\alpha=0.01$  will be used to test this hypothesis. Equivalently, the upper one-sided 99% confidence limit would be less than 1.0.

Adverse Event related efficacy endpoint are defined based on treatment emergency adverse event (TEAE) only, including acute serious bacterial infections, infection other than acute serious bacterial infections, incidence of infections, duration of infections, time to resolution of infection.

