The influence of outliers will be investigated by repeating the primary analysis with any outlying values excluded.

Total amount of follow-up time for each subject is defined as (date of last visit – first infusion date + 1)/365.25 for subjects who complete the study; and defined as (date of withdrawal – first infusion date + 1)/365.25 for subjects who withdraw from the study.

A sensitivity analysis to assess the robustness of the study conclusions to the choice of analysis population will be performed on the PP population and ITT2 population for the primary efficacy variable.

The homogeneity of the treatment effect for a number of important subgroups (i.e. age, sex, race) will be investigated as described in 4.7.1.6.

A by-subject listing of the primary efficacy data will be provided.

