### 4.7.3 Secondary Efficacy Variables

Secondary efficacy endpoints are:

- The incidence of infections other than acute serious bacterial infections meeting FDA guidance criteria.
- The number of days missed from work/school/kindergarten/day care or days unable to perform normal daily activities due to infections.
- The number of days that the care provider of the pediatric subject had to miss work in order to care for the child due to infections.
- The number of days of unscheduled physician visits due to infections.
- The number of days of hospitalizations due to infections.
- The number of days of IV therapeutic antibiotics.
- The number of days of oral (PO) therapeutic antibiotics.
- Time to resolution of infections.
- The incidence of infections other than serious bacterial infections by trough IgG levels. The categories of trough IgG levels will be determined by looking at the distribution of trough IgG levels at the study completion. Incidence will be summarized by total group mean of trough IgG level throughout treatment, including the trough IgG level from infusion 1 to follow up assessment ( $<$  mean Trough IgG,  $\geq$  mean Trough IgG).

These endpoints will be analyzed descriptively by infusion schedule and overall based on ITT and PP populations, respectively. Subject with no experience of specific event will be included in the analysis as zero incidence, zero day, or zero time duration. For hospitalizations, the number and (total) duration for each subject will be calculated and converted to a figure per year. These data will be presented using the standard set of summary statistics (except that the mean and SD will be calculated weighting for the duration of data available for each subject).

Infections is defined as TEAE coded to MedDRA system organ class ‘Infections and infestations’, or otherwise suggestive of an infection by medical review.

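### The per-protocol set requires 12-month completion, so any withdrawal caused by infection takes its events out of that set and weakens it as a robustness check

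*SAP*

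**What the plan says.** SAP section 4.4 makes ITT the main set: "The primary safety and efficacy analysis will be based on the intention-to-treat (ITT) population". ITT takes in every enrolled subject who received any product. PP is the part of ITT "who complete the whole 12-month study period" and without major violations likely to affect the validity of the data. The supplied text makes no exception for subjects who leave because of infection or lack of efficacy.

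PP is used in three places:
- **Primary endpoint (SAP 4.7.2), alongside ITT2:** "A sensitivity analysis to assess the robustness of the study conclusions to the choice of analysis population will be performed on the PP population".
- **Secondary efficacy endpoints (SAP 4.7.3):** "These endpoints will be analyzed descriptively by infusion schedule and overall based on ITT and PP populations, respectively".
- **Fever episodes (SAP 4.7.4):** exploratory, on ITT, ITT2 and PP.

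The success rule in SAP 4.7.1 is a one-sided test at 0.01: "Equivalently, the upper one-sided 99% confidence limit would be less than 1.0". SAP 4.7.2 already gives a follow-up time for subjects who leave early: "date of withdrawal – first infusion date + 1)/365.25 for subjects who withdraw from the study".

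**The concern.** Completion becomes known only after treatment starts, and the endpoint itself can prevent it. A subject who has an SBI and leaves because of it counts in ITT, with the event and the time to withdrawal, but disappears from PP. The trial has a single arm, so no comparator shares the distortion.

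The endpoint does not need the condition. It is a rate per person-year, and partial follow-up is already usable under the SAP's own definition.

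The condition also blurs what the comparison is for. SAP 4.3.2 says that comparing populations shows the impact of major protocol deviations. Withdrawal is not in itself a deviation. With both exclusions in one definition, a difference between PP and ITT cannot be attributed to deviations. What is at stake is the weight a reader can give to PP agreeing with ITT, and the accuracy of the PP columns for the infection-related secondary endpoints.

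**Working it through.** The supplied text gives no assumed SBI rate, dropout rate or power (SAP 4.10 appears only in the contents list), so there is no figure of the plan to reproduce.

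**Inputs from the documents.** Follow-up is 12 months (SAP section 3). At least 42 and up to 50 subjects are planned (protocol synopsis; SAP section 3). The criterion is an upper one-sided 99% limit below 1.0.

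**Assumptions.** The true SBI rate is λ, and each SBI leads to withdrawal with probability p. Neither is given in the documents, so ranges are shown.

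**Step 1: direction.** If SBIs follow a Poisson process and each leads to withdrawal with probability p, completers are exactly the subjects with no withdrawal-causing SBI. Their expected rate is λ(1 − p). The ITT rate, events over time to withdrawal, still estimates λ. At λ = 1.0 and p = 10%, the PP rate is 1.0 × 0.9 = 0.90. The share of subjects lost to an SBI is 1 − exp(−λp) = 1 − exp(−0.10) = 9.5%.

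**Step 2: size at the margin.** Simulation with λ = 1.0 and n = 46, the midpoint (42 + 50)/2, using 5,000 trials per setting. The limit is (k/T) × exp(2.326 × √(φ/k)), where k is events, T is person-years and φ is the Pearson scale estimate. The log link is an assumption.

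| p | Subjects leaving because of an SBI | Mean PP rate | PP meets criterion | ITT meets criterion |
|---|---|---|---|---|
| 10% | 9.5% (about 4 of 46) | 0.90 | 3.9% | 0.5% or less |
| 25% | 22% (about 10) | 0.75 | 19% | 0.5% or less |
| 50% | 39% (about 18) | 0.50 | 65% | 0.5% or less |

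Repeat runs agreed within simulation error. With n = 42 and the exact Poisson limit, χ²(0.99; 2(k+1))/(2T), PP passes in 0.9% of trials at p = 0, 1.7% at 5%, 3.3% at 10% and 64.1% at 50%. ITT stays at 0.7–0.9%.

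**Step 3: dropout unrelated to infection.** With dropout of about 10% a year independent of SBIs, λ = 1.0 and n = 42, completers' rate is 1.00 and PP passes in 0.8% of trials. There is no bias.

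**Step 4: small counts.** Take N = 42, with each withdrawn subject having one SBI at 6 months (assumed), and use the exact limit.
- Two such withdrawals and two SBIs in completers. ITT: T = 40 + 2 × 0.5 = 41, rate 4/41 = 0.098, limit 23.209/82 = 0.283. PP: 2/40 = 0.050, limit 16.812/80 = 0.210.
- Three such withdrawals and no other SBI. ITT: 3/40.5 = 0.074, limit 20.090/81 = 0.248. PP: 0/39 = 0, limit 9.210/78 = 0.118.
- Six such withdrawals and 20 SBIs in completers. ITT: 26/39 = 0.667, limit 81.069/78 = 1.039, fails. PP: 20/36 = 0.556, limit 66.206/72 = 0.920, passes. With N = 50 and the same counts, both pass (0.862 and 0.752).

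At low rates PP can halve the estimate or reduce it to zero without changing the verdict. The verdicts part only near the margin. At a true rate of 0.1, both sets pass in essentially all runs under the exact limit.

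**The case against.** The strongest reply is that nothing is decided on PP. The criterion is applied to ITT, which keeps withdrawn subjects to the date they leave. A reader might take the 65% figure as the trial's false-positive rate. The documents do not support that: in the same simulation ITT passes in 0.5% of trials or fewer, below the nominal 1%.

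A reader might also infer that a favourable PP result is guaranteed by the definition. That does not follow either. The bias needs withdrawal to depend on infection, and the supplied text does not say how often that happens. The 25% and 50% settings are extreme. Planning up to 50 subjects to obtain at least 42 leaves room for (50 − 42)/50 = 16% loss from all causes, and those settings need 22% and 39% from SBIs alone.

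Other points also stand. ITT2 is a second robustness set with no completion condition. The secondary endpoints are reported on ITT as well as PP. Withdrawals are summarised by reason (SAP 4.3.1), and listings show why each subject was left out of each population (SAP 4.4) and the primary efficacy data by subject (SAP 4.7.2), so an SBI in a non-completer can be traced. The supplied text has no content for SAP 4.7.1.3 on dropouts, and protocol sections 4.3 and 9.1.2 appear only in the contents list, so a mitigating rule there cannot be ruled out.

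These points limit the weight of the concern but do not remove it. Listings make the exclusion visible; they do not put the events back into the PP estimate.

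**Conclusion.** The point holds as a modest weakness in a supportive analysis. Where infection causes withdrawal, PP understates the SBI rate and never overstates it for that reason, so its agreement with ITT says little about robustness. In the one simulated setting that fits the planned allowance for dropout (p = 10%), the mean PP rate is 10% too low, and PP would meet the criterion in about 4% of trials at a true rate of exactly 1.0. Larger values of p give larger effects but imply implausibly heavy SBI-driven withdrawal. These sizes rest on an assumed p, a constant SBI rate shared by all subjects, and a true rate at the margin. The primary conclusion does not depend on any of this.

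**What to change.** In SAP 4.4, remove the completion requirement and define PP as ITT subjects without a major violation likely to affect the validity of the data. Count their events and person-time up to withdrawal with the formula already in SAP 4.7.2. There is no need to cut follow-up at the first deviation as well; that would also condition on something that happens after baseline.

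If a completers-only analysis is wanted, keep it as a separate table under that name, with the number of SBIs in excluded ITT subjects shown beside it.

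The cost is one change of definition and the matching programming, with no new data. PP becomes slightly larger, and its rate may be less favourable.

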#### **4.5 Demographic and Other Baseline Characteristics, Medical History and Prior and Concomitant Medications**

Demographic data and baseline characteristics which will be summarized descriptively by infusion schedule and overall for the ITT include age (at screening), sex, race, ethnicity, height (at screening), weight (at screening), duration since first lifetime IGIV infusion, IGIV dose level prior to study enrollment, IgG level prior to first lifetime IGIV infusion, and trough IgG level at most recent IGIV therapy. Demographic and baseline characteristic data will be summarized according to their nature of assessment. No formal testing of demographic or baseline characteristics will be performed. A corresponding listing will be provided.

Partial first lifetime IGIV infusion date will be imputed. When day part of date is missing, year and month part are available, infusion date will be imputed to the first day of the month. When year part is available, both month and day part is missing, infusion date will be imputed to the first day of the year.

For general medical history, all relevant medical conditions will be coded using the Medical Dictionary for Regulatory Activities (MedDRA) dictionary (Version 19.1 or later) and summarized by system organ class (SOC) and preferred term (PT) by infusion schedule and overall, based on the ITT population. An overall by-subject listing will also be provided.

For any recorded medical event medication other than study drugs, medication start and stop dates will be compared to the date of first infusion of study medication to allow medications to be classified as either both Prior and Concomitant or Concomitant only.

If a medication starts before the date of first infusion of study medication and stops on or after the date of first infusion of study medication then the medication will be classified as both Prior and Concomitant. Medications will be classified as Concomitant only if they have a start date on or after the date of first infusion of study medication.

If medication start and/or stop dates are missing or partial, the dates will be compared as far as possible with the date of first infusion of study medication. Medications will be assumed to be Concomitant only, unless there is clear evidence (through comparison of partial dates) to suggest that the medication started prior to the first infusion of study medication. If there is clear evidence to suggest that the medication started prior to the first infusion of study medication, the medication will be assumed to be both Prior and Concomitant.

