	
(21(±4 days) or 28(±4 days) days) within 12 months prior to study treatment.
 
 
5. Subject is willing to comply with all requirements of the protocol.
 
6. Females of child-bearing potential with a negative pregnancy test at screening and females who agree to employ adequate birth control measures during the study.
 
7. Males who agree to practice adequate birth control measures during the study.
 
8. Subject, parent or guardian has signed the informed consent form and an assent form for children (≥ 2 to < 12 years of age at study entry) and adolescents (≥ 12 to < 17 years of age at study entry) as appropriate per study documentation and regulations of the local jurisdiction.
 
9. Authorization to access personal health information.
 
10. Subject currently participating in a clinical trial with another experimental IGIV may be enrolled if he/she has received stable IGIV therapy for at least 3 infusion cycles prior to receiving GC5107 and all inclusion and exclusion criteria are satisfied. 
 
• Other IGIVs will be prohibited for an infusion cycle (21(±4 days) or 28(±4 days) days) prior to the first infusion of GC5107 until the completion of Follow-up visit.
 
 
 
11. Subject currently participating in a trial of subcutaneous immunoglobulin (SCIG) can be enrolled if he/she is switched to IGIV for three infusion cycles (21(±4 days) or 28(±4 days) days) prior to enrollment in this study.
 

EXCLUSION CRITERIA
	
 
1. Subject has secondary immunodeficiency.
 
2. Subject was newly diagnosed with PHID and has not yet been treated with immunoglobulin.
 
3. Subject has been diagnosed with dysgammaglobulinemia or isolated IgG subclass deficiency or isolated IgA deficiency with known anti-IgA antibodies.
 

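### SAP 4.5: the rule for incomplete medication dates has no outcome for a drug that clearly stopped before the first GC5107 infusion, so it labels that drug concomitant and contradicts the complete-date rule (minor)

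*SAP*

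**What the plan says.** SAP 4.5 sets the aim of the classification: "medication start and stop dates will be compared to the date of first infusion of study medication to allow medications to be classified as either" one of two labels, Prior and Concomitant together, or Concomitant only.

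For complete dates there are two rules.

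- The combined label needs both an earlier start and a stop that is not earlier: a drug that began before the first infusion and "stops on or after the date of first infusion of study medication then the medication will be classified as both Prior and Concomitant".
- The other label depends on the start: "Medications will be classified as Concomitant only if they have a start date on or after the date of first infusion of study medication".

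For incomplete dates, a further paragraph of 4.5 opens with "If medication start and/or stop dates are missing or partial, the dates will be compared as far as possible with the date of first infusion". Two outcomes follow. The default is Concomitant only. If comparison of the partial dates gives clear evidence that the drug began before the first infusion, then "the medication will be assumed to be both Prior and Concomitant". Neither outcome carries a condition on the stop date.

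The revision history records that version 2.0 of the SAP dropped the separate analysis of medications that were prior only. This explains why the current text has no such label.

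**The concern.** Whether a drug was taken during GC5107 treatment depends on when it stopped. An unknown start day does not alter a stop date already known to precede the first infusion. Under 4.5, however, that unknown start day moves the record from the complete-date rule, which does not call the drug concomitant, to the incomplete-date rule, which does.

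What is at stake is the accuracy of the concomitant-medication summaries and listings. A short antibiotic or corticosteroid course that ended before the study would be shown as on-study use because one element of a date was not recorded. The reader of the report would then be told about treatment during the study that did not occur.

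**Working it through.** The plan states no figure on this point, so there is nothing to reproduce. The check sets the two rules side by side and applies them to example dates.

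**The rules as conditions.** Let S be the start, E the stop and F the first infusion.

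- Complete dates: S ≥ F gives Concomitant only. S < F and E ≥ F gives Prior and Concomitant. S < F and E < F gives no label.
- Incomplete dates: S clearly < F gives Prior and Concomitant. Anything else gives Concomitant only. E appears in neither condition.

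**Application.** F = 15 Aug 2017 is assumed for illustration only. A stop counts as provably earlier when the latest date it allows is before F. An earlier stop is accepted as evidence of an earlier start, because a drug cannot start after it stops.

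| Pattern | Start | Stop | Provably stopped before F? | Label under 4.5 as written |
|---|---|---|---|---|
| 1 | 1 Mar 2015 | 20 Jul 2017 | Yes | None (complete dates) |
| 2 | 2015 | 20 Jul 2017 | Yes | Prior and Concomitant |
| 3 | Mar 2015 | 20 Jul 2017 | Yes | Prior and Concomitant |
| 4 | missing | 20 Jul 2017 | Yes | Prior and Concomitant |
| 5 | 1 Mar 2015 | Jul 2017 (latest 31 Jul) | Yes | Prior and Concomitant |
| 6 | 2017 | 20 Jul 2017 | Yes | Prior and Concomitant |
| 7 | 1 Mar 2015 | missing | No | Prior and Concomitant |
| 8 | 2015 | 1 Sep 2017 | No | Prior and Concomitant |
| 9 | missing | missing | No | Concomitant only |

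**Reading the table.**

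- Patterns 2 to 6 are the five with an incomplete date and a provably earlier stop. All five are labelled concomitant.
- Pattern 1 has the same stop date as patterns 2 to 4 and 6, but complete dates, and is not labelled concomitant. This is the contradiction.
- In patterns 4 and 6 the start date alone does not show an earlier start. A programmer who did not infer it from the stop would assign Concomitant only, which is equally wrong.
- Patterns 7 to 9 have a later or unknown stop. Pattern 8 is labelled correctly, and 7 and 9 follow a normal conservative assumption.

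**With the stop condition restored.** If the incomplete-date rule also required that the stop not be clearly before F, patterns 2 to 6 would join pattern 1 outside the concomitant group. Patterns 7 to 9 would not change.

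**The case against.** The strongest reply is that the incomplete-date paragraph does not ignore stop dates: its opening sentence says start and/or stop dates will be compared as far as possible. A sensible programmer might read the paragraph as filling in what is unknown within the complete-date scheme, and not as overriding a stop date that is known. Defaulting to concomitant under uncertainty is also the cautious choice for safety review.

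Part of this stands. It would be too strong to say that the stop date is disregarded, and the default is sound when the stop is missing, ongoing or ambiguous. But the opening sentence attaches no result to an earlier stop. The only evidence the paragraph acts on concerns the start, so following the text gives the wrong label.

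A reader might also draw three stronger conclusions. The documents do not support them.

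- *Previous IGIV would appear as on-study use.* SAP 4.5 does say "Partial first lifetime IGIV infusion date will be imputed", but that sentence serves a baseline characteristic (time since the first lifetime IGIV infusion) and has its own imputation rule. The text available treats previous IGIV as baseline variables. Nothing says that it is classified under the medication rule.
- *False prohibited-medication flags would distort the per-protocol set.* SAP 4.3.2 has deviations identified by the clinical study team, with exclusions defined in a separate deviation specification. SAP 4.4 adds a data review meeting. Neither names this label as an input. The body text of SAP 4.5.1 and Protocol 5.14.2, both on prohibited medications, was not available to check.
- *The primary results are affected.* SAP 4.7.2 and 4.8.1 describe the primary efficacy and safety analyses without any use of this label.

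**Conclusion.** The rule is wrong as written, and the matter is minor. For medications with an incomplete date and a stop clearly before the first GC5107 infusion, the incomplete-date rule in SAP 4.5 contradicts the complete-date rule and assigns a concomitant label that the recorded stop date disproves.

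Only those records are affected, and the consequence that can be shown is extra entries in descriptive concomitant-medication outputs. How many there would be cannot be estimated, because the documents do not say how often dates are incomplete.

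The conclusion assumes that the outcome sentences are programmed as they stand. If the programming already treats a known earlier stop as decisive, the outputs will be right and only the text needs correcting. Days of IV and oral therapeutic antibiotics are secondary endpoints (SAP 4.7.3). The available text does not say whether they draw on this label, so the sponsor should confirm that they do not.

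**What to change.** Add one sentence to SAP 4.5: a medication whose stop date, or the latest date that a partial stop date allows, is before the first GC5107 infusion is not concomitant and is listed only. Keep the present default when the stop is missing, ongoing, or could fall on or after the first infusion. This brings the two rules into line without restoring a summary of prior-only medications.

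Do not use the label to remove records from prohibited-medication review. Inclusion criterion 10 in the Protocol synopsis says "Other IGIVs will be prohibited for an infusion cycle" before the first GC5107 infusion as well as during the study, so a product stopped before that infusion can still fall inside the prohibited window. That review must compare actual dates with its own window.

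The cost is one sentence and a small programming change. There is no real downside.
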